13.4.4 Analyses of Secondary and Other Endpoints

The key secondary endpoint for Part 2 is complete response at 48 weeks, defined as an IgG4-RD RI Score of 0 and a glucocorticoid dose of 0 mg/day and no flare since beginning treatment. A fixed sequence testing procedure will be conducted with the primary efficacy endpoint, to control the overall Type I error rate at 0.05. Specifically, if the between-group comparison of disease response at 48 weeks reaches statistical significance, a comparison of the rates of complete remission at 48 weeks will be performed using a Fisher's Exact test with a two-sided Type I α of 0.05. If the between-group comparison of disease response at 48 weeks fails to reach statistical significance,

inferences on complete remission will be supportive without overall Type I error control. The proportion in complete remission in each arm will be reported with two-sided 95% Clopper-Pearson confidence intervals. All participants in the mITT population who drop out of the study prior to reaching week 48 for any reason, including a disease flare, initiation of non-protocol therapy, or any other reason to cause them to be unevaluable using the IgG4 Responder Index, will be defined as not achieving complete remission.

All inferential analyses for the additional secondary efficacy endpoints are considered supportive; p-values for test of differences among groups will be presented without adjustment for multiple comparisons. All secondary endpoints will be analyzed in the mITT and PP populations, and in the subgroup with elevated serum IgG4 level prior to initiation of study therapy.

For all dichotomous efficacy endpoints, Fisher's Exact tests will be conducted and two-sided 95% Clopper-Pearson confidence intervals will be reported.

Frequency counts of the number of disease flares and the number of organ sites with disease-related damage will be reported by arm, and between-group comparison will be performed using Fisher's Exact Test.

For secondary continuous efficacy endpoints, including the Physician Global Assessment and Patient Global Assessment, descriptive statistics will be used to summarize the distribution of scores in each arm. The absolute change from baseline will be analyzed using an analysis of covariance model (ANCOVA) with treatment allocation as the independent variable.

Treatment group differences for the safety endpoints will be compared using a Fisher's exact test.

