3.3 Secondary Endpoints

Part 2: Key Secondary Efficacy Endpoint

1. Complete remission at 48 weeks, defined as an IgG4-RD RI Score of 0 and a glucocorticoid dose of 0 mg/day and no flare since beginning treatment.

Part 1 and Part 2: Additional Secondary Efficacy Endpoints

1. The proportion of participants that reach the following threshold levels of IgG4-RD RI improvement at 48 weeks: 50% and 75%.
2. Number of disease flares, as defined in Section 3.5.3.
3. Change in PhGA from baseline.
4. Change in PGA from baseline.
5. Disease-related damage, as measured by the damage section of the IgG4-RD RI.

Part 1 and Part 2: Secondary Safety Endpoints

1. The proportion of participants who experience at least one Grade 2 or higher adverse event.
2. The proportion of participants with a Grade 3 or higher infection.
3. The proportion of participants who experience a malignancy.
4. The proportion of participants who experience a Hepatotoxicity, defined as increase in the aspartate aminotransferase (AST) or alanine aminotransferase (ALT) to elevations three times the upper limit of normal.
5. The proportion of participants who experience a serious adverse event.
6. The proportion of participants who experience infusion reactions, defined as any adverse reaction within 24 hours of infusion which are Grade 2 or higher events and at least possibly related to study drug.

Part 2: Secondary Safety Endpoint

1. The proportion of participants who experience at least one Grade 3 or higher adverse event.

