3.5.3 Disease Flare Definition

Disease flare will be defined as recurrence of disease activity such that additional immunosuppressive therapy beyond the trial protocol is indicated. Such additional therapy may include glucocorticoids or alternative immunosuppressive agents. At the time of a potential disease flare, investigators will document the features of the disease flare by performing the assessments outlined in the **Flare Documentation Guidance (Appendix 5: Flare Documentation Guide)**. A disease flare must be reported by the site investigators to the Division of Allergy, Immunology, Transplantation – Statistical and Clinical Coordinating Center (SCCC) within 24 hours of discovery (Section 12.5.2).

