6.6 Premature Discontinuation of Investigational Agent

Study treatment will be discontinued for any participant who experiences any of the following:

- Pregnancy
- Any Grade 4 or higher infection
- For AEs associated with laboratory evaluations, any of the following lab abnormalities that persist longer than 5 days:
 - i. eGFR < 30 ml/minute/1.73m²
 - ii. WBC ≤ 1.5 x 10⁹/L
 - iii. Platelet count < 50 x 10⁹/L
 - iv. Hemoglobin < 8 g/dL
 - v. ANC < 1.0 x 10⁹/L
 - vi. ALT or AST elevation > 5 times ULN
 - vii. Total bilirubin > 3 times ULN. If Gilbert's disease, total bilirubin > 3 times baseline value.
- For AEs associated with clinical evaluations, any Grade 3 or higher event as defined by the National Cancer Institute-Common Terminology Criteria for Adverse Events (NCI-CTCAE) that is possibly, or definitely related to elotuzumab including anaphylaxis (see **Appendix 7: Clinical Criteria for Diagnosing Anaphylaxis**)[39] or infusion reaction
- Malignancy excluding squamous cell and basal cell carcinoma of the skin
- Disease flare, as defined in Section 3.5.3
- Participants who decide to discontinue the treatment
- The investigator believes that the study treatment is no longer in the best interest of the participant.

Participants will be expected to remain in the study for follow up despite discontinuation of study drug. Participants who discontinue protocol-specified treatment requirements will be treated as medically indicated according to physician discretion.

7 Concomitant Medications

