13.4.2 Primary Analysis of Primary Endpoint

Part 1

Descriptive statistics will be used to summarize the proportion of participants in each cohort who experience at least one Grade 3 or greater adverse event during study participation for all participants in the safety population. The primary analysis of efficacy and safety endpoints will be conducted after all participants in Cohort 1a and 1b complete the Week 48 assessments or are withdrawn from the study.

Part 2

The primary endpoint for Part 2 is disease response at 48 weeks, defined as the percent improvement in the IgG4-RD RI score over baseline:

$$\% \text{ Improvement in IgG4RD RI}_{\text{Week 48}} = 100 * \left(\frac{\text{IgG4RDRI}_{\text{Baseline}} - \text{IgG4RDRI}_{\text{Week 48}}}{\text{IgG4RDRI}_{\text{Baseline}}} \right)$$

For participants whose IgG4-RD RI score is worse (e.g. higher) at week 48 than baseline, their % Improvement in IgG4-RD RI_{Week 48} will be considered 0%. Additionally, participants who use glucocorticoids or other immunosuppressants beyond that permitted by protocol, or who experience a disease flare as defined in Section 3.5.3 at any time point before 48 weeks will be defined as achieving no disease response (0%).

The observed levels of disease response at 48 weeks will be summarized by arm in the mITT population as the median, interquartile range, and range. A between-group comparison of the assessment of disease response at 48 weeks will be performed using a Wilcoxon-Mann-Whitney test with a two-sided Type I α of 0.05, and will be reported with a two-sided 95% confidence interval for the Mann-Whitney parameter (Section 13.6) derived under the proportional odds assumption [41]. The primary analysis of disease response will treat all participants who drop out of the study prior to reaching week 48 for any reason, including a disease flare, initiation of non-protocol therapy, or any other reason to cause them to be unevaluable using the IgG4 Responder Index, as having no disease response (0% improvement) for the primary endpoint. The primary analysis will be conducted after all participants in Cohort 2 complete the Week 48 assessments or are withdrawn from the study.

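### Complete remission lacks the primary endpoint's rule on non-protocol immunosuppression, so a Week 48 completer can score 0% on the primary and still count as in remission

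*Combined protocol and SAP*

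**What the plan says.** The synopsis, 3.3 and 13.4.4 give the same three conditions for complete remission at Week 48. In 13.4.4 they read "an IgG4-RD RI Score of 0 and a glucocorticoid dose of 0 mg/day and no flare since beginning treatment". The endpoint is tested by a two-sided Fisher's exact test at 0.05 in the mITT population, in fixed sequence after the primary. It is the only secondary endpoint with Type I error control.

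The primary endpoint rule in 13.4.2 assigns a 0% response before Week 48 to "participants who use glucocorticoids or other immunosuppressants beyond that permitted by protocol, or who experience a disease flare as defined in Section 3.5.3". Therapy use and flare are joined by an or, so either is enough.

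Section 13.4.4 has its own non-remission rule. It names non-protocol therapy, but only for mITT participants "who drop out of the study prior to reaching week 48 for any reason".

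Three other sections bear on who that rule reaches:
- **3.5.3** defines a flare as "recurrence of disease activity such that additional immunosuppressive therapy beyond the trial protocol is indicated".
- **6.6** keeps participants in the study after study drug is stopped and adds: "Participants who discontinue protocol-specified treatment requirements will be treated as medically indicated according to physician discretion". Section 11.1 likewise follows Part 2 participants to Week 48 whether or not study medication has been stopped.
- **7.3** treats prohibited medication as a protocol deviation unless it is given for a flare. Section 7.2 permits two short glucocorticoid courses for other indications, completed at least 8 weeks before the Week 48 visit.

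**The concern.** The two efficacy endpoints in the fixed sequence handle the same event differently. Under 13.4.2, non-protocol immunosuppression makes a participant a non-responder. Under 13.4.4, it matters only if it comes with a flare, a non-zero glucocorticoid dose at Week 48, or dropout.

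A participant who avoids all three and reaches an RI of 0 counts as a complete remission, although other immunosuppression may have contributed. The remission rate then no longer describes elotuzumab (or placebo) plus the prednisone taper alone, and the two endpoints disagree about the same person. A decision on such a case made after unblinding could settle a Type I-controlled result.

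**Working it through.** **1. The plan's own figure.** Section 13.7 states an exact power of 0.826 for 25% vs 65% with 21 and 42 participants. Enumerating Binomial(42, 0.65) × Binomial(21, 0.25) and rejecting when the two-sided Fisher p ≤ 0.05 gives 0.8261. The figure reproduces. The point is about the definition, not the sample size.

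**2. The two rules side by side, for a participant who completes Week 48.**

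| Event before Week 48 | Primary (13.4.2) | Complete remission (3.3, 13.4.4), if RI is 0 and dose is 0 mg/day at Week 48 |
|---|---|---|
| Flare under 3.5.3 | 0% | Not in remission |
| Non-protocol glucocorticoids, stopped before Week 48, no flare | 0% | In remission |
| Other non-protocol immunosuppressant, no flare | 0% | In remission |

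The last two rows disagree. The dropout sentence in 13.4.4 does not change them, because these participants complete Week 48. Section 13.4.2 has a dropout sentence as well as the separate therapy rule; 13.4.4 has only the dropout sentence.

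**3. Ways into those rows.**
- Study drug is stopped for an adverse event or laboratory rule (6.6), and an immunosuppressant is started at physician discretion for a reason other than recurrence.
- A glucocorticoid course exceeds the 7.2 limits in number, length or timing but ends before Week 48. Without a flare it is only a deviation under 7.3.
- Therapy is added for disease that persisted. Read literally, 3.5.3 requires recurrence, so this is not a flare. This is the most interpretive route, and the point does not depend on it.

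**4. Size per participant.** 1/42 = 2.4 percentage points on elotuzumab; 1/21 = 4.8 on placebo.

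**5. Effect on the test (two-sided Fisher, elotuzumab vs placebo).**

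Near the boundary, one participant is enough:
- 22/42 vs 5/21: p = 0.035
- 21/42 vs 5/21: p = 0.060 (one fewer on elotuzumab)
- 22/42 vs 6/21: p = 0.107 (one more on placebo)

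At about the design rates (0.65 × 42 = 27.3; 0.25 × 21 = 5.25):
- 27/42 vs 5/21: p = 0.003
- three fewer on elotuzumab, 24/42 vs 5/21: p = 0.016
- five fewer, 22/42 vs 5/21: p = 0.035
- six fewer, 21/42 vs 5/21: p = 0.060

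**6. Sensitivity under an assumed rate.** The documents do not say how many participants would qualify. Assume 0 to 10 percentage points per arm, added to strict rates of 25% and 65%:

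| Added on placebo / elotuzumab (points) | Power |
|---|---|
| 0 / 0 | 0.826 |
| 5 / 0 | 0.691 |
| 10 / 0 | 0.534 |
| 5 / 5 | 0.812 |
| 10 / 10 | 0.823 |
| 0 / 5 | 0.907 |

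If both strict rates are 25%, the Fisher test alone rejects with probability 0.035. Adding 5 points to one arm makes this 0.049 (elotuzumab) or 0.054 (placebo); adding 10 makes it 0.095 or 0.106. These figures ignore the requirement that the primary succeed first.

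**The case against.** **Most rescue is already covered.** This stands. Extra immunosuppression for recurrent disease is a flare under 3.5.3, and a flare excludes remission. A reader might infer that rescued participants in general can count as remissions; the documents do not support that. What remains is non-flare use and, on a literal reading, therapy for disease that never remitted.

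**The intent is visible.** By naming non-protocol therapy in its non-remission rule, 13.4.4 suggests that such cases were meant to be failures. That makes this a drafting gap, but the rule as written stops at dropouts. Section 13.4.3 defers details of the supportive analyses to the Statistical Analysis Plan, and 13.5.2 defers the safety reports. Neither defers the remission definition.

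**The per-protocol analysis would show a discrepancy.** Partly so. Section 13.4.1 requires adherence to the glucocorticoid-course limit, and its masked review considers changes in concurrent therapy. But the controlled test is in mITT, and a second population does not correct it.

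**The effect may be small.** This stands too. At the design rates it takes six one-sided reclassifications (6/42 = 14% of the arm) to lose significance, and the test is confirmatory only after a primary that already applies the strict rule.

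**Does the gap favour elotuzumab?** A reader might infer so, because drug-related stops should be commoner on that arm. The documents do not establish it. The laboratory stopping rules in 6.6 apply to both blinded arms, and therapy for persistent disease could be commoner on placebo.

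**Do the 50% and 75% thresholds share the gap?** No separate gap is shown. They are thresholds of RI improvement, the variable to which 13.4.2 already attaches the 0% rule.

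**Conclusion.** The gap is real and follows from the text alone. Complete remission has no condition on non-protocol immunosuppression in participants who complete Week 48, whereas the primary has one. The same person can be a 0% responder and a complete remission in the mITT analysis.

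The scope is limited to use that is not a flare under 3.5.3. The size is 2.4 points per participant on elotuzumab and 4.8 on placebo, and it is decisive only when the result is near the significance boundary. How many such participants there will be, and in which arm, is unknown. The scenarios above rest on an assumed range and show sensitivity, not expected bias. The case for correction is that this is the only Type I-controlled secondary endpoint and its definition should be settled before unblinding.

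**What to change.** In the synopsis, 3.3 and 13.4.4, add that "participants who use glucocorticoids or other immunosuppressants beyond that permitted by protocol" before Week 48 are not in complete remission, whether or not they drop out. This is the existing 13.4.2 wording, so the two endpoints would then agree. If the sponsor intends them to differ, the protocol should say so and give the reason before unblinding.

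The clause depends on what counts as permitted. Section 7.2 allows two short glucocorticoid courses for other indications, while the per-protocol definition in 13.4.1 refers to a single permitted course. Those passages need to be reconciled so that the clause has one meaning.

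For the 50% and 75% endpoints, it is enough to confirm that they use the 13.4.2 response variable.

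Cost: one sentence in three places. Concomitant medications are already collected (3.6.4, 13.4.5), so no new data are needed. The observed remission rate may be slightly lower. If 25% and 65% are read as rates under the strict definition, the stated power of 0.826 is unchanged.

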Secondary Endpoints	
Part 2: Key Secondary Efficacy Endpoint
 
 1. Complete remission at 48 weeks, defined as an IgG4-RD RI Score of 0 and a glucocorticoid dose of 0 mg/day and no flare since beginning treatment. 
Part 1 and Part 2: Additional Secondary Efficacy Endpoints
 
 1. The proportion of participants that reach the following threshold levels of IgG4-RD RI improvement at 48 weeks: 50% and 75%. 2. Number of disease flares, as defined in Section 3.5.3, by 24 and 48 weeks. 3. Change in PhGA from baseline. 4. Change in PGA from baseline. 5. Disease-related damage, as measured by the damage section of the IgG4-RD RI at 24 weeks. 
Part 1 and Part 2: Secondary Safety Endpoints
 
 1. The proportion of participants who experience at least one Grade 2 or higher adverse event. 2. The proportion of participants with a Grade 3 or higher infection. 3. The proportion of participants who experience a malignancy. 4. The proportion of participants who experience a Hepatotoxicity, defined as an increase in the aspartate aminotransferase (AST) or alanine aminotransferase (ALT) to elevations three times the upper limit of normal. 5. The proportion of participants who experience a serious adverse event. 6. The proportion of participants who experience infusion reactions, defined as any adverse reaction within 24 hours of infusion which are Grade 2 or higher events and at least possibly related to study drug. 
Part 2: Secondary Safety Endpoint
 
 1. The proportion of participants who experience at least one Grade 3 or higher adverse event.
Exploratory Endpoints	
Part 1 and 2: Exploratory Endpoints
 
 1. Serum immunoglobulin levels, IgG subclass concentrations, IgE levels, eosinophils, and serum C3 and C4 levels. 2. ELF score (see Section 3.5.7). 3. Blood concentrations of T cells and B cell subsets of interest, specifically: 
 a. CD4+ cytotoxic T lymphocytes b. CD8+ cytotoxic T lymphocytes c. CD4+ T follicular helper cells

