2.4 Secondary Objectives

1. To compare the effect of the addition of elotuzumab versus placebo to prednisone on complete remission at 48 weeks.
2. To compare the effect of the addition of elotuzumab versus placebo to prednisone on the number of disease flares (as defined in Section 3.5.3) per participant over time.
3. To compare the effect of the addition of elotuzumab versus placebo to prednisone on the change from baseline in Physician Global Assessment (PhGA) at 4, 8, 12, 16, 20, 24, 28, 32, 36, 40, 44, and 48 weeks.
4. To compare the effect of the addition of elotuzumab versus placebo to prednisone on Patient Global Assessment (PGA) at 4, 8, 12, 16, 20, 24, 28, 32, 36, 40, 44, and 48 weeks.
5. To compare the effect of the addition of elotuzumab versus placebo to prednisone on safety.

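### The flare comparison in Section 13.4.4 uses neither individual follow-up nor flare times beyond the Week 24 and 48 cut-points, so it does not match secondary objective 2

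*Combined protocol and SAP*

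**What the plan says.** Secondary objective 2 (Section 2.4) compares the arms on "the number of disease flares (as defined in Section 3.5.3) per participant over time". The synopsis lists the endpoint as "Number of disease flares, as defined in Section 3.5.3, by 24 and 48 weeks", while Section 3.3 lists only "Number of disease flares, as defined in Section 3.5.3", without a time point.

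For the analysis, Section 13.4.4 states: "Frequency counts of the number of disease flares and the number of organ sites with disease-related damage will be reported by arm", and then "between-group comparison will be performed using Fisher's Exact Test". It does not say whether the table is any flare versus none or 0/1/2+ flares. It names no person-time, rate or time-to-event method and gives no rule for participants who withdraw before Week 48. Such rules are written out for the primary endpoint (13.4.2) and for complete remission (13.4.4).

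The same section sets the status of the test: "All inferential analyses for the additional secondary efficacy endpoints are considered supportive". Section 6.6 lists "Disease flare, as defined in Section 3.5.3" among the reasons for ending study treatment. Section 11.1 keeps participants in follow-up to Week 48 after study medication stops.

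**The concern.** An objective worded per participant and over time calls for a method that knows how long each participant was observed. A Fisher test on counts does not. Without a withdrawal rule, a participant who leaves in Week 6 without a flare contributes the same zero as one who is flare-free for 48 weeks. If withdrawal differs between arms, the arm that loses more people looks better.

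Flare timing is also a main clinical signal here. Prednisone ends at Day 69 (Section 7.1.1.3) and infusions run to Week 40, so what is tested over most of follow-up is maintenance of control. The first flare is the cleanest event for that purpose, because study treatment stops at a flare and the Section 3.5.3 definition implies other therapy.

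**Working it through.** **The plan's own figures.** The only Fisher power in the documents is for complete remission (Section 13.7): 25% vs 65%, 21 vs 42 participants, two-sided 0.05, stated as 0.826. Full binomial enumeration gives 0.8261, so the arm sizes and the test are reproduced. No power is stated for flares.

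**Inputs for flares.** From the documents: 42 elotuzumab and 21 placebo participants, 48 weeks. Assumed: two-sided 0.05, constant flare and dropout hazards, and all flare and dropout rates. The 39% and 12% pair comes from Section 1.1.2 (relapse on prednisone alone and failure on a cyclophosphamide combination). These are background rates, not Part 2 projections. Fisher's test is applied to any flare versus none.

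**Equal dropout, 10% per arm (simulated rejection rates).** Pearson's chi-square is included because it also ignores timing and follow-up. It therefore separates Fisher's conservatism from the information lost.

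| Flare risk, elotuzumab vs placebo | Fisher | Chi-square | Log-rank |
|---|---|---|---|
| 12% vs 39% | 0.60 | 0.67 | 0.69 |
| 20% vs 50% | 0.60 | 0.67 | 0.69 |
| 25% vs 55% | 0.56 | 0.64 | 0.67 |
| 25% vs 60% | 0.68 | 0.76 | 0.79 |
| 39% vs 39% (null) | 0.032 | 0.054 | 0.051 |

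Log-rank minus Fisher is 0.09 to 0.11. Log-rank minus chi-square is only 0.02 to 0.03. Over wider assumed rates and 0–20% dropout, these gaps run from about 5 to 13 points and about 1 to 4 points. A log-rank test stratified by disease status behaves alike: 66–77% against 56–67% for Fisher at 10% dropout, with null size about 5%.

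**Unequal dropout.** Let p be the true 48-week flare risk and d the dropout risk, with λ = −ln(1−p) and μ = −ln(1−d). The expected crude flare proportion is λ/(λ+μ) × [1 − (1−p)(1−d)].

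- Placebo, p = 0.55, d = 0.30: 0.799/1.155 × (1 − 0.45 × 0.70) = 0.691 × 0.685 = 0.474.
- Elotuzumab, p = 0.25, d = 0.05: 0.288/0.339 × (1 − 0.75 × 0.95) = 0.849 × 0.2875 = 0.244.
- The true difference of 0.30 shrinks to 0.474 − 0.244 = 0.230. Fisher's power is about 0.39 and the log-rank's about 0.64. For 12% vs 39% with the same dropout, the powers are about 0.46 and 0.66.
- Equal true risk of 0.40, with d = 0.30 vs 0.05: 0.589 × 0.58 = 0.34 against 0.909 × 0.43 = 0.39. The arm losing more participants gains a spurious 5 points.
- Reversed, with d = 0.30 on elotuzumab and 0.05 on placebo, and p = 0.25 vs 0.55: 0.446 × 0.475 = 0.212 against 0.940 × 0.5725 = 0.538. The apparent difference is 0.326, larger than the true 0.30. Enumeration at these proportions gives Fisher a rejection rate of about 0.69. It can then exceed the log-rank, but only because the comparison is biased towards elotuzumab.

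**The case against.** The strongest reply is that little hangs on this test. It is declared supportive, carries no multiplicity-controlled claim and has no stated power. Flare and dropout already count against a participant in the primary endpoint (0% response) and in complete remission, so the confirmatory results are not exposed. Follow-up continues after study drug stops, so unequal follow-up arises only from withdrawal, loss to follow-up or death. All of this stands and limits the weight of the point.

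Three stronger readings are tempting, and the documents do not support them.

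- *Ignoring timing costs about 10 power points.* The chi-square comparison shows that most of the gap is Fisher's discreteness. The total depends on rates that the documents do not give, and on constant hazards although all participants take prednisone for the first ten weeks.
- *A flare at Week 12 counts the same as one at Week 47.* Under the synopsis, the first counts at both cut-points and the second only at Week 48. The statement fits only Section 3.3, which omits the time points.
- *The plan declares dropouts flare-free.* It does not. It is silent, and zero flares is what an unadjusted count then yields.

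It is also fair to say that time to first flare is not the stated endpoint, which is a number of flares. A remedy that dropped the count would replace the endpoint, so the count must stay. Section 13.4.3 refers to a separate Statistical Analysis Plan for further detail on supportive analyses of the primary endpoint; if that plan also covers flares, it may settle some of this.

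**Conclusion.** The mismatch between objective 2 and the planned test is in the text and needs no assumption: the test uses no individual follow-up, no flare times beyond two cut-points and no withdrawal rule. Its cost in power is conditional on the assumed rates. With similar withdrawal in both arms it is moderate, and it comes mainly from Fisher's null rejection of about 3%. The better reason to change is unequal withdrawal, which biases the crude proportions in either direction. The 20 to 25 point gap applies when placebo loses far more participants than elotuzumab; the 5% and 30% are illustrative, not forecasts. A reader might infer that a confirmatory conclusion is at risk. It is not, since the flare comparison lies outside the fixed testing sequence.

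**What to change.** In Section 13.4.4:

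1. Make time to first flare (mITT population) the between-arm comparison: a two-sided log-rank test stratified by newly-diagnosed or relapsing disease, a Cox hazard ratio with 95% CI, and Kaplan-Meier flare-free proportions at Weeks 24 and 48. Censor at study withdrawal, not at the stop of study drug.
2. Keep the number of flares as an endpoint. Report it by arm with a rate adjusted for follow-up, and state the count categories of any frequency table.
3. Give Section 3.3 the Week 24 and Week 48 time points of the synopsis.

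The cost is wording only. Flares are already reported within 24 hours of discovery (Sections 3.5.3 and 12.5.2), and the stratum is already used in randomization (Section 3.7). There are three small downsides. The log-rank test is asymptotic, although its simulated size here is about 5%. Time to first flare does not use later flares, which follow the stop of study drug and other therapy. Censoring assumes that withdrawal is unrelated to flare risk, so reasons for withdrawal should be tabulated by arm. The analysis remains supportive.
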